5.6 BLINDING

At the end of the Baseline Period, subjects who qualify to enter the study will be randomized to receive ZX008 0.2 mg/kg/day, ZX008 0.8 mg/kg/day (maximum dose: 30 mg/day), or placebo and assigned a randomization number by the IVR/IWR system. Once a randomization number is assigned to a subject, the site will record the subject's initials on the corresponding study drug labels. Each bottle will contain the assigned treatment (ZX008 or placebo) and the ZX008 and placebo solutions will be identical.

The blinding scheme instituted for this study will ensure that the volume of study medication taken cannot be associated with the dose group, thus unblinding the study. This is achieved by random assignment of different concentrations of the ZX008 oral solution (1.25 mg/mL, 2.5 mg/mL, and/or 5 mg/mL) by the IVR/IWR system. The IVR/IWR system will instruct site personnel to the volume of oral solution to be administered based on that subject's weight. (Dose will be recalculated by the system once at the midpoint of the study.) During the Titration, Maintenance, and Taper/Transition Periods, the subjects and study personnel (investigators, clinical staff, personnel involved in data collection and analysis, the Medical Monitor, and the sponsor) will be blinded to the treatment allocation and to the concentration of ZX008 oral solution. If an investigator feels the blind should be broken, he/she can do so when necessary for treatment decisions. However, the investigator should endeavor to discuss with the Medical Monitor or Sponsor's Medical Representative, if available. The blind should only be broken in the event the knowledge of whether the subject is on active study medication versus placebo is needed to determine course of medical treatment for the event. The subject will be discontinued from the clinical trial upon breaking of the blind and the decision whether the subject can enter the separate open-label extension study will rest with the Sponsor if the subject exited Study 1501 prior to completion.

5.7 PRIOR AND CONCOMITANT MEDICATION

All medications taken by a subject during the Screening and Baseline Seizure Assessment Periods are regarded as prior therapy and must be documented in the eCRF. Significant medications (e.g., antibiotics) taken within 30 days prior to the Screening visit should also be captured. All prior and concomitant AEDs will be collected in the CRF.

Confidential Page 48 of 182

All medications taken by a subject after the first administration of IMP are regarded as concomitant medication and must be documented in the eCRF, including over-the-counter medication, herbal and vitamin/supplement preparations. Subjects are required to take at least one concomitant AED during the study. All subjects will continue to receive their existing AED(s) with the same doses throughout the study. Every effort should be made to ensure that the regimen of existing medications remains stable during the study; any changes must be discussed with the sponsor prior to implementation. If a decrease in a concomitant AED is necessary to manage an AE, this must be discussed with the sponsor as soon as possible after implementation if not before implementation. Non-study medications and therapies that are considered necessary for the subject's welfare and will not interfere with the response to the study medication may be given at the discretion of the investigator, informing the Medical Monitor as soon as possible.

It should be noted for any subject receiving hypoglycemic agents, the investigator should consider diabetic medication changes in the setting of weight loss and hypoglycemia.

5.7.1 Vagal Nerve Stimulation

Subjects receiving treatment with a VNS may be included as long as the VNS has been in place for at least 6 months prior to entry into the study, the VNS battery is not due for replacement during the study, and stimulation parameters have been kept constant for 4 weeks prior to screening and must remain so throughout the study. The subject's use of VNS will be recorded in the CRF.

5.7.2 Ketogenic Diet

Adherence to the KD, or a modified version of KD, is permitted during the study if the dietary habits were initiated more than 4 weeks prior to Screening and remain stable throughout the study. The subject's use of KD will be recorded in the CRF.

5.7.3 Rescue Medication for Seizures

The subject's usual or prescribed regimen and frequency of rescue therapy for seizures should be entered into the prior and or concomitant medication sections of the eCRF.

Use of rescue medication is permitted during the study and should be recorded on the eCRF (day, medication[s], dose[s]) and in the diary (day, timeframe associated with seizure episodes). Repeated administrations within the same episode should be recorded separately.

5.7.4 Prohibited Concomitant Medication and Food

A list of medications/foods that are to be avoided as ongoing medications or for chronic use if initiated during the study from the time of signing the informed consent form (ICF) until the end-of-study visit (or early termination) is provided in Appendix 1. If medical necessity requires short-term use of one or more of these medications during the course of the study, please contact the Medical Monitor for approval.

The following concomitant medications are prohibited during the clinical trial:

Confidential Page 49 of 182

- AEDs: Phenytoin, carbamazepine, oxcarbazepine, eslicarbazepine, retigabine/ezogabine
- Stiripentol (STP): Subjects must be off STP for a minimum of 21 days prior to the Screening visit.
- Felbamate is prohibited as a concomitant medication unless the subject has been on felbamate for at least 18 months prior to screening, has stable liver function and hematology laboratory tests, and the dose is expected to remain constant throughout the study.
- Drugs that interact with central serotonin, including but not limited to: imipramine
 monoamine oxidase inhibitors, selective serotonin reuptake inhibitors, serotoninnorepinephrine reuptake inhibitors, vortioxetine
- Drugs that increase cardiovascular risk including: atomoxetine and those with noradrenergic reuptake properties (NRIs, SNRIs)
- Drugs intended to facilitate weight loss
- Other: any form of marijuana, THC and derivatives (including Epidiolex®)
- A list of medications/foods that are to be avoided as ongoing medications or for chronic use if initiated during the study from the time of signing the informed consent form (ICF) until the end-of-study visit (or early termination) is provided in Appendix 1. If medical necessity requires short-term use of one or more of these medications during the course of the study, please contact the Medical Monitor for approval.

5.8 TREATMENT COMPLIANCE

Each subject or parent/caregiver will record the dose, dosing frequency and IMP consumption in the subject's diary. Subjects will bring their used, partially used, and unused IMP to every study visit. Treatment compliance will be monitored by measuring the volume of IMP in these bottles and comparing to the dispensation log and diary records.

6. VISIT SCHEDULE

Study procedures will be conducted according to the Schedule of Assessments in Table 1. Time windows for all assessments are detailed in Table 6.

Table 6: Time Windows for Assessments

Visit / Procedure	Time window (relative to scheduled visit / procedure)
Visit 1 (Clinic; Study Day -43 to -42 or -42 to -41):	Not applicable
Visit 2 (Phone; Study Day -21)	± 3 days
Visit 3 (Clinic; Study Day -1; Randomization)	+ 4 days ^a
Visits 4, 5 (Phone: Study Days 4, 8)	± 3 days
Visit 6 (Clinic; Study Day 15)	± 4 days
Visit 7 (Phone: Study Day 29)	± 4 days
Visit 8 (Clinic; Study Day 43)	± 4 days

Confidential Page 50 of 182

Visit 9 (Phone: Study Day 57)	± 4 days
Visit 10 (Clinic; Study Day 71)	± 4 days
Visit 11 (Phone: Study Day 85)	± 4 days
Visit 12 (Clinic: Study Day 99)	± 4 days
Visit 13 (Clinic; Study Day 113; post dosing)	± 4 days
Visit 14 (ECHO clinic; 3-6 months after last dose)	+ 30 days
Blood collection for ZX008 PK	± 15 minutes
Blood collection for AED concentration	Prior to morning dose of AED medication

AED=antiepileptic drug (s); ECHO=echocardiogram; PK = pharmacokinetics

6.1 BASELINE PERIOD (STUDY DAY -42 TO STUDY DAY -1)

The Baseline Period of the study encompasses the screening activities that will occur on Study Day -42 as well as the observation period where subjects will be assessed for baseline seizure activity based on recordings of daily seizure activity entered into a diary.

6.1.1 Screening, Clinic Visit 1 (Study Day -42)

Screening is the predetermined series of procedures with which each investigator selects an appropriate and representative sample of subjects for enrollment into the study. Select screening data will be documented in the IVR/IWR and eCRF.

Written informed parental or guardian consent and assent of minors (if the subject is capable of providing assent) must be obtained before a subject can start any of the screening procedures. The procedure(s) for obtaining written informed consent and assent of minor (if the subject is capable of providing assent) are described in Section 112.

The Screening visit will occur on Study Day -42; however, the procedures may be split over 2 consecutive days (e.g., Study Day -43 and Study Day -42 or Study Day -42 and Study Day -41). Splitting the visit procedures across 2 nonsequential days requires the approval of the medical monitor. The following procedures will be performed for all subjects before the start of seizure activity observation:

- Obtain written informed consent for the study
- Obtain written informed consent from parent/caregiver to collect PedsQL Family Impact, HADS, and EQ-5D-5L ratings of parent/caregiver symptoms and quality of life
- Review inclusion and exclusion criteria
- Record demographic information
- Record medical, neurological, and epilepsy history
- Record current epilepsy status (number/type/duration seizures per month)
- Collect past 6 months (or available duration) of parent/caregiver seizure diary data if Confidential Page 51 of 182

a In cases where the screening period is extended beyond 42 days, the immediate 42 days before the Randomization visit will be used to calculate the baseline seizure frequency

available (screen shots of cell phones are acceptable, as are photocopies of paper diaries or print outs) and place in source file

- Record prior medications
- Complete physical examination, including height, weight, and calculation of BMI
- Complete neurological examination
- 12-lead electrocardiogram
- Doppler ECHO (this may be obtained any time between Study Day -42 and Study Day -21)
- Vital signs
- Urine pregnancy test for females of child-bearing potential
- Laboratory evaluation (serum chemistry, hematology, urinalysis, etc)
- Urine THC panel
- Whole blood CBD
- Obtain blood sample for epilepsy genotype panel
- C-SSRS Children's Baseline/Screening Assessment (Appendix 2)
- Instruct parent/caregiver on use of diary
- Dispense diary (after above procedures have been concluded)
- Record AEs
- Record AESIs

Only eligible subjects as specified by the inclusion and exclusion criteria with an independently confirmed diagnosis of DS by the Epilepsy Study Consortium will be enrolled into the study.

After enrollment into the study, each subject will be issued a "Subject Card" containing information about the subject's participation in the study. The subject or parent/caregiver will be advised to retain this card on his person for the entire duration of the study so that the investigator or the sponsor can be contacted in case of emergency.

In certain circumstances the sponsor may allow subjects who did not meet all inclusion/exclusion criteria at the time of the Screening Visit to have the screening period extended, or to be re-screened for eligibility. In all cases the investigator should consult with the Medical Monitor. Decisions whether to permit rescreening resides solely with the sponsor.

The decision whether to permit extended screening or rescreening can be influenced by many

Confidential

Page 52 of 182

factors individual to that subject case. Some general principles apply:

- 1. If baseline seizure screening is extended or the subject is discontinued and then rescreened, the screening period for establishing the baseline seizure frequency will be the immediate 6 weeks before the randomization visit.
- 2. Subjects who are found to be on a prohibited medication at the screening visit may be weaned off of that medication provided:
 - a. Decisions to withdraw a disallowed concomitant medication must be made with the agreement of the prescribing physician
 - b. If the medication has antiepileptic properties, a wash out of at least 5 half-lives must be completed before collection of baseline seizure data.
 - c. If a decision has been made to wean off of a medication without antiepileptic properties and the wash-out period (at least 5 half-lives) is expected to be shorter than 5 weeks, then the subject may remain in screening and chart seizures using the seizure diary.

6.1.2 Phone Visit 2 (Study Day -21)

Site personnel will contact the subject via telephone on Study Day -21 and record the following:

- AEs
- AESI

In addition, site personnel with review the diary entries with the parent/caregiver.

6.1.3 Clinic Visit 3 (Study Day -1): Randomization

This period is intended to ensure that subjects meet the study entry criteria and confirm they have experienced ≥6 convulsive seizures during the 6-week Baseline Period, with at least 2 seizures in each 3-week half of the Baseline Period. Subjects must have at least 42 days of prospective diary data at Visit 3. Subjects will report to the clinic in the morning on Study Day -1 to allow for plasma sample collection for AED pharmacokinetic evaluation prior to the morning dose of these medications. Subjects should not take their morning dose(s) of AED medication prior to reporting to the clinic.

The following procedures will be performed on Study Day -1:

- Review inclusion and exclusion criteria
- Review current seizure activity (number/type/duration) from diary since previous visit and calculate the number of convulsive seizures during the first 3 weeks, the second 3 weeks, and over the full 6-weeks of the observation period.

Confidential Page 53 of 182

- Record prior medications since previous visit
- Complete physical examination, including height and weight, and calculation of BMI
- Abbreviated neurological examination
- Vital signs
- 12-lead ECG
- Urine pregnancy test for females of child-bearing potential
- Laboratory evaluation (serum chemistry, and hematology, and urinalysis)
- Collect plasma sample for AED pharmacokinetic evaluation prior to the morning dose of study medication(s)
- Urine THC panel
- Whole blood CBD
- Tanner Staging for subjects >7 years of age (Appendix 5)
- Collect and review diary with parent/caregiver
- Dispense diary
- C-SSRS Children's Since Last Visit Assessment (Appendix 2)
- BRIEF (Appendix 3)
- QOLCE (Appendix 4)
- PedsQL (Appendix 6)
- PedsQL Family Impact module (Appendix 6)
- Parent/Caregiver QoL using the EQ-5D-5L scale (Appendix 7)
- Affective symptoms of parent/caregiver using the HADS scale (Appendix 8)
- Record AEs
- Record AESI
- When eligibility for the Titration Period is confirmed, randomize (blinded) subject to treatment assignment (ZX008 0.2 mg/kg/day, ZX008 0.8 mg/kg/day, or placebo)
- Dispense study medication (If administration of the first dose of study medication occurs in the clinic, the next dose should be at least 8 hours later or the following

Confidential Page 54 of 182

morning. The dose on the following morning will count as Study Day 1.)

6.2 TITRATION AND MAINTENANCE PERIODS

6.2.1 Titration Period Study Day 1

Subjects will take their first dose of study medication on the morning of Study Day 1. Study Day 1 is considered the first day of dosing, even for those subjects that received an in-clinic dose on Study Day -1.

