- b: Subjects who are discontinued early and those who complete the study and choose not to enroll in the separate open-label extension will be tapered off study medication over an up to 2-week period.
- c: Follow-up ECG, ECHO, and physical examination will be performed 3-6 months after early termination, or for those subjects who complete the study but do not enter the open-label extension study (see Section 6.4).
- d: The Visit 8 ECHO must be performed any time between Study Day 40 and Study Day 54. The Visit 12 ECHO must be performed any time between Study Day 90 and Study Day 113; if a subject discontinues early from the study, the ECHO should be scheduled as soon as practical. If the Study Day

Confidential Page 23 of 182

- 43 ECHO was completed < 30 days prior to early termination, the Visit 12 ECHO will not be performed provided the parent/guardian agrees to bring the subject to the clinic for the cardiac follow-up visit.
- e: Females of child-bearing potential
- f: Plasma sample for pharmacokinetic assessment will be conducted prior to the dose at Visit 8 and 1, 2, and 4-6 hours after dose administration.
- g: Plasma sample for assessment of background AED(s) will be conducted prior to the dose of AED(s) at Visits 3, 6, 8 and 12.
- h: Study drug/diary dispensed for the Transition Period for subjects entering the open-label extension study and for the Taper Period for subjects exiting the study.
- i: Site personnel will review study medication dosing procedure (titration) with parent/caregiver.
- j: Study drug administration begins in the morning of Study Day 1.
- k: Only adverse events related to cardiac safety will be collected at this visit.
- l: Mandatory one time collection any time during or after screening.

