10.4 TREATMENT PERIODS

Baseline Period

The Baseline Period covers the approximately 42-day span just prior to randomization and the start of treatment. The baseline frequency of convulsive seizures will be calculated from data collected during this period.

Titration Period

The Titration Period covers the first 14 days of treatment while subjects are titrated to their randomized dose. It begins on the first day of treatment (Study Day 1) and extends through Study Day 15 regardless of the exact day on which a subject reaches his or her assigned dose. The Titration Period applies to all subjects including placebo recipients.

Maintenance Period

The Maintenance Period covers the 12 weeks following the end of the titration period. It begins on Study Day 16 and extends through Study Day 99.

Titration + Maintenance (T+M) Period

The T+M period combines the Titration and Maintenance periods, beginning on Study Day 1 and extending through Study Day 99. The T+M period is considered the treatment period.

Confidential Page 84 of 182

Follow-up Period

The Follow-up Period begins immediately at the end of T+M period and extends to a final visit 2 weeks later; i.e., from Study Day 99 through Study Day 113. Only subjects who do not roll over enrollment into the open-label extension will participate in the Follow-up Period.

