10.5.2 Safety Analyses

Summaries of safety data will be presented by treatment – ZX008 0.8 mg/kg/day, ZX008 0.2 mg/kg/day or placebo – separately for the Titration, Maintenance and T+M periods. The number and percentage of subjects in each treatment group with AEs will be displayed by body system and preferred term using the Medical Dictionary for Regulatory Activities (MedDRA). Summaries of AEs by severity and relationship to study drug will also be presented. A separate summary will be provided for all serious AEs (SAEs). Selected summaries will be repeated broken out by age group, i.e., for ages <6 years and ≥6 years.

Hematology and chemistry laboratory results will be summarized using shift tables that tabulate the proportion of subjects who have lab results that change from baseline. Shift tables will be presented for each time point where lab results are collected. Mean change from baseline will also be calculated for continuous hematology and chemistry results at all time points available.

Laboratory tests, vital signs, physical examinations, neurological examinations, ECG, Doppler echocardiogram, C-SSRS, Tanner Staging results, etc, will be summarized appropriately, by treatment. All safety summaries will be based on the SAF Population.

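### Adverse events after an in-clinic first dose on Day -1 fall outside every on-treatment safety summary, because treatment is declared to start on Day 1

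*Protocol*

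**What the plan says.** **When dosing can start.** Section 6.1.3 (Visit 3, Day -1) ends with dispensing and adds: "If administration of the first dose of study medication occurs in the clinic, the next dose should be at least 8 hours later", or the next morning. One dose, possibly two, can therefore precede Study Day 1.

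**When dosing is said to start.** Section 6.2.1 first states that "Subjects will take their first dose of study medication on the morning of Study Day 1", then covers the exception: "Study Day 1 is considered the first day of dosing, even for those subjects that received an in-clinic dose on Study Day -1". Table 1 footnote j gives the default without the exception: "Study drug administration begins in the morning of Study Day 1".

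**Analysis periods.** Section 10.4 says of the Titration Period: "It begins on the first day of treatment (Study Day 1"). It ends on Day 15, Maintenance covers Days 16 to 99, and T+M covers Days 1 to 99 and is named as the treatment period. Section 10.5.2 presents safety "separately for the Titration, Maintenance and T+M periods".

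**Baseline.** The heading of Section 6.1 places it at "BASELINE PERIOD (STUDY DAY -42 TO STUDY DAY -1"). Section 10.4 instead describes a span of about 42 days that precedes both randomization and the start of treatment. Table 6 footnote a, for extended screening, uses the 42 days before the Randomization visit.

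**The concern.** Sections 6.2.1 and 10.4 set the start of treatment by calendar convention rather than by exposure. For a subject dosed in clinic, the first hours on drug come before the declared start of treatment, and the safety tables are built on periods that begin at that declared start. First exposure is when an acute reaction would be expected to show. Section 8.8 lists hypersensitivity among the events needing report within 72 hours, and comparing safety with placebo is a stated objective (Section 2.4). If ZX008 causes any first-dose effect, leaving those hours out of the tables understates it.

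The second issue is the baseline boundary. If Day -1 counts as baseline in full, some on-drug diary time would be treated as untreated.

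**Working it through.** **Step 1. Place the post-dose hours of Day -1.**

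| Period | Span | Source | Contains post-dose Day -1? |
|---|---|---|---|
| Baseline, by study day | Day -42 to -1 (42 days) | 6.1 | Yes |
| Baseline, statistics section | before randomization and treatment start | 10.4 | No |
| Baseline, extended screening | 42 days before Randomization visit | Table 6, footnote a | No |
| Titration | Day 1 to 15 | 10.4 | No |
| Maintenance | Day 16 to 99 (84 days) | 10.4 | No |
| T+M | Day 1 to 99 | 10.4 | No |

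The last three rows are the only periods named in Section 10.5.2, and none contains these hours. Under Section 10.4 the hours fall in neither baseline nor T+M. Under Section 6.1 they fall in baseline.

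**Step 2. Compare the anchors.** The Safety Population (10.2.1) requires one dose. Concomitant medication (5.7) begins at the first IMP administration. Section 8.6 defines pre-treatment serious events by first exposure to IMP. All three use actual exposure, whereas Sections 6.2.1 and 10.4 use Day 1. A subject who took only the Day -1 dose would be in the Safety Population, with the only dosing outside every safety period.

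**Step 3. Size on safety.** The gap is one part-day per subject dosed in clinic. The share dosed in clinic is not given. If it were 10%, 50% or 100% of the 105 planned subjects (assumptions), that is 10.5, 52.5 or 105, so about 11, 53 or 105 first-dose days. The 100% case is only a ceiling, since Section 6.2.1 and footnote j make Day 1 the default.

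**Step 4. Size on efficacy, if Section 6.1 is followed.** The plan's own figure comes first (Section 10.1: difference 40 points, SD 50, two-sided 0.05, 35 per arm, 90% power).
- Normal approximation: n = 2 × (1.960 + 1.282)² × 50² / 40² = 32.8, so 33 per arm.
- Power at 35 per arm is 91.7% (normal) or 91.0% (noncentral t). The t-based minimum is 34. The stated 35 reproduces.

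Now let f be the on-drug fraction of Day -1, e the seizure suppression in that time, and r the true reduction; f, e and r are assumptions. The baseline rate is read as b = (42 − f·e)/42 of its true value, and the observed reduction is 1 − (1 − r)/b.
- Extreme case, f = 1 and e = 1: b = 41/42, so baseline is 1/42 = 2.4% too low. With r = 40%, 1 − 0.60 × 42/41 = 38.5%, a shift of −1.5 points. With r = 60%, 1 − 0.40 × 42/41 = 59.0%, a shift of −1.0 point.
- Milder case, f = 0.5 to 0.6 and e = 0.4 to 1.0: baseline is 0.5% to 1.4% too low and the shift is −0.2 to −0.9 points.
- If the extreme 1.5 points came off the whole planned difference (38.5 instead of 40), power at 35 per arm would be 88.8% (t) or 89.6% (normal).

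Any seizure suppression on Day -1 lowers the active arms' baseline, so the shift runs against ZX008.

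**The case against.** The case against is strong on three readings that a reader might infer.

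**That on-drug time counts as baseline.** This rests on the Section 6.1 heading. The analysis text in Section 10.4 and Table 6 footnote a both point to time before randomization, and a dose can only follow randomization. Eligibility cannot be affected, because the seizure count is completed before the subject is randomized. The documents support a disagreement about the boundary, not a settled rule that contaminates baseline. The effect would be trivial and conservative in any case.

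**That first-dose reactions are lost.** They are not. Adverse events are collected from consent (8.4), serious events are reported within 24 hours (8.6), and hypersensitivity goes to the Medical Monitor within 72 hours (8.8). The synopsis display of adverse events names no period. Nothing says that such an event must be dated to baseline. Only the period-based tables of Section 10.5.2 are affected.

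**That Study Day 1 should be redefined as the date of the first dose.** The titration steps in Section 5.5.2 and Table 3 are keyed to Study Day, so renumbering would bring dose escalation forward by a calendar day for subjects dosed in clinic. That changes treatment and is not needed to repair an analysis period.

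It can also be said that the Day 1 rule is a deliberate convention, stated in both 6.1.3 and 6.2.1, and that treatment emergence is usually defined in the SAP. The first is true of numbering, but a numbering convention need not decide which events count as on treatment. The second would excuse silence. Here the protocol itself fixes the start of treatment and the safety periods, so an exposure-based SAP definition would have to depart from it.

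**Conclusion.** Wrong as written, minor. Followed literally, Sections 6.1.3, 6.2.1, 10.4 and 10.5.2 together leave adverse events that begin after an in-clinic dose on Day -1 outside every on-treatment safety summary, while Sections 10.2.1 and 5.7 already use the actual first dose. The gap is confined to one part-day in subjects dosed in clinic, whose number is not stated.

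The disagreement between 6.1 and 10.4 over baseline is real but immaterial to efficacy: at most 1 of 42 days, and about 1.5 points or less for true reductions of 40% or more. This assumes that the drug suppresses rather than provokes seizures on that day, and takes the percentage-change scale of Section 10.1. The case for a change therefore rests on safety reporting and internal consistency, not on the primary analysis.

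**What to change.** For analysis only:
- Start the on-treatment adverse-event period, and with it the Titration and T+M safety summaries, at the date and time of the first IMP administration, wherever it is given.
- State that baseline seizure frequency uses only diary data from before that dose.
- Leave Study Day numbering, visit days and the titration schedule unchanged.
- Reconcile Sections 6.1, 6.1.3, 6.2.1, 10.4 and 10.5.2 and Table 1 footnote j with this single anchor.

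The cost is a few sentences and one date-time derivation. The one new demand on sites is that the time of any dose on Day -1 must be captured, so that events and diary entries that day can be placed before or after it.
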